We will describe the baseline characteristics of the 'effectiveness' cohort, and the second-line treatment pathways. We will evaluate the relative effectiveness of each second-line treatment strategy incorporating the subsequent treatments that patients receive in current practice. This aspect of the study will be designed according to the target trial framework.⁴¹ In brief, a target trial is a hypothetical RCT for assessing comparative effectiveness from observational data which requires the definition of the main elements of a trial's protocol, including eligibility criteria and the respective treatment strategies. We will apply target trial principles⁴¹ to primary care data in England between 2015-2021 from the CPRD to identify people with T2DM who had similar prognosis prior to initiating any of the three second-line antidiabetic drug treatments under comparison.

Workshop

We will convene a design workshop to inform the proposed analysis. The panel of health care professionals and PPI representatives will advise on: the definition of personalisation; the choice of subgroup variables, building on those identified in the literature review; the communication of the risks and benefits of the alternative treatments; and the prioritisation of the different outcome measures. The clinical panelists will include diabetologists, GPs and practice nurses involved in care for people with T2DM. The majority of the PPI panellists will be people with T2DM who have experienced second-line treatment. Diabetes UK and local PPI panels convened by the co-applicants have agreed to support the study and participate in the workshops (see PPI section for full details).

Outcomes

The primary outcome will be the absolute change in HbA1c (mmol/mol) between baseline and 1-year following each second-line treatment prescription (HbA1c at 1-year – HbA1c at baseline). Treatment groups will be compared according to the mean change in HbA1c. We will use the measurement closest in time to the 1-year follow-up timepoint and allow for measures within ±90 days, otherwise the measure will be designated as missing.

Secondary outcomes will include: change in HbA1c at 2-years, and change in BMI, SBP, and eGFR all at 1and 2-years. We also reported the time to the following first events before 2-years follow-up: (a) a 40% decline in eGFR from baseline, which could be a marker for the rarer end-stage kidney disease (ESKD) outcome,²² (b) a major adverse kidney event (MAKE), a composite outcome for the earliest of a decline in eGFR from baseline of 40%, ESKD, and all-cause mortality,(c) heart failure hospitalisation, (d) 3-point major adverse cardiovascular event (MACE), a composite outcome for the earliest of myocardial infarction, stroke, and CVD death, and (e) all-cause mortality. We also reported time to myocardial infarction and stroke individually.

Sample size calculation

The study will include approximately 25,700 (SU=6000, DPPi4=13,000, SGLT2i=6,700) patients who meet the eligibility criteria. The FDA recommends that an average between-treatment difference in the HbA1c change from baseline of 0.4% (e.g. from 8.0% to 7.6%) is of clinical significance⁴². The assumed standard deviation of 2.4 is taken from a previous study of patients with T2DM recruited from CPRD⁴³. We follow methodological recommendations for sample size calculations with IV designs, by assuming a 'base case' level of non-compliance of 10%, but also consider scenarios with alternative levels¹. We require 90% power at the 5% (2-sided) level of statistical significance. We follow methodological recommendations for sample size calculations with IV designs, it will not perfectly predict the treatment received, and so we assume the 'base case' compliance (the proportion of patients in who actually receive the treatment predicted by the IV) is 80%, but also consider scenarios where the V is weaker (70% compliance) and stronger (90%). Table 1 shows the requisite sample sizes for the two treatment groups projected to have fewest patients (SU and SGLT2i). The anticipated sample sizes will be more than sufficient across these scenarios for detecting whether the overall estimates of treatment effectiveness are statistically significant.

With the projected sample sizes, we can also report estimates of treatment effectiveness with sufficient precision for major subgroups of prime interest, for example according to established CVD (or not), and broad categories by age, and levels of baseline HbA1c, and eGFR.

	Level of	compliance (IV strengt	th)		
70%			80)%	909	%
Effect size: between-treatment difference in mean HbA1c reduction baseline to 12 months	SU	SGLT2i	SU	SGLT2i	SU	SGLT2i
0.3	3416	1464	2615	1121	2066	886
0.4	1921	823	1471	630	1162	498
0.5	1230	527	941	403	744	319

Table 1: Required sample size (N) for the IV design according to instrument strength (level of compliance) and magnitude of effect size at 90% power and 2.5% (2-sided) level of statistical significance

Analysis

An instrumental variable (IV) analysis will address confounding by indication. The instrumental variable approach taken will be the two-stage residual inclusion (2SRI) method.²³ This approach will enable us to report comparative effectiveness across the full study populations of interest, that is, to report average treatment effects, while addressing the risk of bias from unmeasured confounding. The first stage models will estimate the probabilities for each person to be prescribed each treatment given their baseline covariates and their CCG's tendency to prescribe (TTP) that treatment. The second-stage outcome models will include generalised residuals from the first stage (propensity score) models. The outcome models will be estimated by ordinary least squares (OLS) for continuous outcomes (e.g. 1-year HbA1c), and Cox proportional hazards models for time-to-event outcomes.⁴⁵ All standard errors will be calculated with non-parametric bootstrapping, and will account for clustering of individuals within practices, and within- individual correlation introduced by repeated measures of outcomes.

Sensitivity analyses

We will undertake sensitivity analyses to consider data issues, for example by applying alternative exclusion criteria for when there is doubt about the clinical coding of T2DM⁴⁶ or the second-line treatment regimen. We will consider different assumptions about missingness patterns, for example by undertaking complete records analysis⁴⁷. We will examine the robustness of the findings to alternative statistical models including those that use traditional IV designs and risk-adjustment.

Output

We will provide estimates of the comparative effectiveness of second-line treatments with SUs vs DPP4is vs SGLT2is.

Objective 3: To examine heterogeneity in the comparative effectiveness of DPP4i versus SU

We will design a second target trial to examine if comparative effectiveness of alternative second-line treatments for people with T2DM differs across patient subgroups (treatment effect heterogeneity). We will limit the scope of this investigation to the comparison of SU vs DPP4is and for the primary outcome (mean change in HbA1c between baseline and 1-year follow-up). The rationale for these choices are that it will enable us to compare the estimated treatment effects with those from a published RCT.⁴⁸ We will limit the cohort inclusion criteria to presenting for second-line treatment in years 2011 to 2015, as over this period the use of SGLT2i is low, and the vast majority of prescriptions for second-line treatment for T2DM in England are for SU or DPP4i.

We will again combine the target trial design with an IV analysis that could reduce the risk of confounding and assess treatment effect heterogeneity. We will use a different form of IV approach to the previous paper, in that we will use a local instrumental variable (LIV) method.^{49,50} This approach will enable us to fully examine treatment effect heterogeneity including treatment effect modification according to levels of unobserved covariates (essential heterogeneity) across subpopulations that would –and would not– have met the eligibility criteria for the published RCT. Using the CCG's TTP DPP4i as instrument and the same covariates as in the 2SRI case in WP2, the LIV method can identify individualised treatment effects. These individual effects will then be aggregated to report average treatment effects across the full target population (defined by a national

clinical guideline), and for the 'RCT-eligible' and 'RCT-ineligible' subpopulations. Within the LIV estimation, the first-stage models will estimate the probability that each person is prescribed DDP4i given their baseline covariates and their CCG's TTP. The second-stage outcome models will then include the predicted probabilities from the first-stage (propensity score) models, covariates, and their interactions. For the RCT-eligible population we will compare the average treatment effect to those from the published RCT.

Output

We will provides assessments of heterogeneity in the comparative effectiveness of second-line treatments with SUs vs DPP4is across whole populations of interest, including those who do not meet RCT eligibility criteria

Objective 4: Comparative effectiveness according to age, baseline HbA1c, and individual risk-factor profiles of multiple long-term conditions (MLTCs).

To further assess treatment effect heterogeneity, we will assess the extent to which the relative effectiveness of the alternative second-line treatments differs according to age, baseline HbA1c, and the presence of different MLTC. It is possible that factors related to living with MLTC, for example, polypharmacy, could modify the treatment effects estimated in RCTs which tend to include healthier people living with fewer long-term conditions (LTC) compared with the general population of people with T2DM. Thus, we will investigate heterogenous treatment effects for the three second-line oral antidiabetic treatments of interest in the PERMIT study (SU, DPP4i, and SGLT2i, all added to metformin monotherapy) according to diverse MLTC and patient characteristics.

We will revert back to the three-way comparison of second-line treatments, since the potential for heterogeneous treatment effects is of interest for all three comparisons, particularly SGLT2i versus DPP4i and SU. The LIV approach cannot be used for the three-way treatment comparison and so we will use the 2SRI approach (see also objective 2). We will use the same primary outcome as for the overall comparative effectiveness study that is the mean change in HbA1c between baseline and 1-year follow-up.

Output

We will provide further assessments of heterogeneity in the comparative effectiveness of alternative second-line treatments according to age, baseline HbA1c and presence of MLTCs.

Objective 5: Calibrate RAPIDS microsimulation model to UK data and use resultant RAPIDS-UK model to predict probabilities of long-term complications for people with T2DM in England after second-line treatment with SU, DPP4i or SGLT2i added to metformin

The RAPIDS model predicts levels of intermediate outcomes over time, including HbA1c; BMI; serum highdensity lipoprotein (HDL); low-density lipoprotein (LDL); and total cholesterol; serum triglycerides; SBP; DBP and eGFR (see Figure 4).²⁹ This model estimates probabilities of all-cause death and other clinical events, such as advanced diabetic eye disease, hypoglycaemia, myocardial infarction (MI), unstable angina, stroke, heart failure (HF), lower-extremity amputation (LEA), and ESKD. The inputs required by RAPIDS to estimate such probabilities include a mixture of constant risk factors (sex and ethnicity), and time-updated (over each 90-day quarter) risk factors, such as age, duration of diabetes, treatments prescribed (glucose-lowering agents, statins, and blood pressure-lowering drugs), and histories of CVD and hypoglycaemia.

We will extend the RAPIDS microsimulation model for a T2DM population in England to predict long-term outcomes following the initiation of one of the three second-line antidiabetic therapies of interest. This model will recognise diverse treatment patterns observed in routine clinical practice. We will calibrate predicted values and assess the external validation of RAPIDS when the model is applied to CPRD data.⁵¹ We will compare the predicted outcomes across the alternative second-line treatments over a maximum follow-up of 7.6 years. We will calculate the between-treatment differences in the means of these predictions together with 95% CI. We will report the comparative effectiveness of these alternative second-line treatments on these long-term

outcomes, both overall and stratified by baseline CVD status. We will implement RAPIDS in R 4.3.1.

Outputs

We will provide an individual-level simulation model for T2DM that accurately predicts long-term outcomes according to the risk profile of general populations of people with T2DM in the UK presenting for second-line treatment. We will provide estimates of the comparative effectiveness of the alternative treatments according to long-term outcomes.

[figure not shown]

Fig. 4. The real-world progression in diabetes (RAPIDS) model. Glucose-lowering duotherapy includes dual combinations of oral antidiabetic drugs. The right hand box represents transitions over time periods. For particular events (e.g. Myocardial Infarction) the model allows patients to progress to a healthy state in the period following the event (left hand column). For other sequelae (e.g ESRD) the patient remains in that chronic disease state in the period following the event.

5.Dissemination, knowledge mobilisation and pathways to impact

Findings will be presented at UK and international conferences about diabetes care. The design and translation workshops will draw on the views of patient representatives, GPs, practice nurses, national policy makers (e.g. NICE, NHS England), to help ensure the study can inform future clinical guidelines and care for patients with T2DM. We will work closely with colleagues at NICE from the outset to ensure that the study design is defined to ensure the results can input directly into future clinical guidelines for T2DM. The research will provide recommendations via the Academic Health Sciences Networks to commissioners and providers of T2DM care on targeting second-line treatment regimens to individual patients, and those patient groups where additional evidence would be of greatest value.

While the study will use CPRD-HES data from the UK, we will ensure that both the empirical and methodological insights have wider relevance. We will work with an advisory panel (see below) to consider carefully the implications of the findings to other countries. The methods will be discussed at academic meetings, in particular, the international conference in Medical Decision-Making and the UK Health Economists' Study Group.

We will develop a study website that will be an important repository of information about the study methods and findings, for both lay and professional audiences. It will include study protocols, and early 'heatmaps' conveying the study findings. We will make a version of the long-term effectiveness model available on the project website. The website will reside within the main LSHTM website (e.g. permit.lshtm.ac.uk) and will be developed by the research manager, and then maintained by the research administrator.

6.Plans to engage patients, NHS and wider population about the work

The application has benefited from the input of co-applicant [name], a Patient Research Ambassador Initiative member, and member of the NIHR HTA commissioning board, and [name], a patient with T2DM. The PPI representatives felt that the study design and interpretation should be informed by experiences of patients with T2DM, and have supported plans for two workshops which will include PP representatives. The first (design) workshop will inform the way personalisation is defined, and the prioritisation of the different outcome measures, and the second (translation) workshop will focus on interpretation and communication of results.

We will work with the LSHTM media department, and our lay representatives to ensure the findings are accessible to the broader public. The study website will be an important repository of information about the study methods and findings, for both lay and professional audiences. A full and complete account of the research will be made available by open access as a publication in the NIHR HTA Journal. Research papers will be published in peer-reviewed journals.

7.Project/research timetable

Grant Start date: January 2020

6 Months prior	Development of initial study protocols		
to grant start	University ethics application and approval		
to grant otart			
Months 0-9	Application and receipt of CPRD data		
	Data cleaning, testing of provisional drug coding algorithms consistent		
	with GOLD and Aurum CPRD data, and VA data (US)		
	Extraction of HES admissions according to ICD-10 codes		
	Preparation of summary data for discussion at clinical/PPI panel		
Month 6	Clinical/PPI panel to refine subgroup definitions, prioritisation of		
	outcomes (Design workshop)		
Month 9	Advisory Group Meeting		
	Finalisation of study protocols and analysis plans		
	Approval of final amendments to ethics applications		
Months 9-12	Application of final coding algorithms to full CPRD-HES linked data		
	Submission of paper to Health Economics Study Group on IV design		
	Final study protocols, study design publications in open access journals		
Months 13-18	Inequalities analysis (obj 1)		
	Submit paper I		
Month 12	Interim report to NIHR		
Months 13-28	comparative effectiveness analysis (obj 2)		
	submit paper II		
Month 24	Interim report to NIHR		
Month 27	Advisory Group meeting		
Month 29-36	Heterogeneity analysis (obj 3)		
	Submit paper III		
Month 36	Interim report to NIHR		
Month 37-44	MLTC analysis (obj 4)		
	Submit paper IV		

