- a) By Clinical Commissioning Group in 2014 (n = 4,450 patients).
- *b)* By year across all Clinical Commissioning Groups (n = 61,787 patients).

Year intensifying treatment from metformin monotherapy

Patient-level covariates (see also outcomes)

For the one-year period *prior* to second-line treatment, we will extract information on patient characteristics (age, gender, ethnicity, index of multiple deprivation, marital status, approximate duration of diabetes), comorbidities (e.g. established CVD, CHF, CKD), and biomarker levels (HbA1c, high-density lipoprotein (HDL) cholesterol, low-density lipoprotein (LDL) cholesterol, total cholesterol, triglycerides, other systolic blood pressure (SBP), diastolic blood pressure (DBP), eGFR, body weight, and BMI). Each of these measures will be considered as part of the measurement of the baseline risk profile, and following the findings of the literature review and the design workshop, will be considered as variables for the subgroup analysis and in reporting results according to baseline risk profiles. The list of patient-level covariates

includes all those that will be required by the RAPIDS-UK model for predicting long-term effectiveness (see objective 5).

Treatment use

To address the research questions, the RAPIDS-UK model will require information on each patient's full longitudinal patterns of antidiabetic treatments, and those of concomitant medications for lipid lowering and anti-hypertensives. First, the model requires information on the drugs prescribed for the period *prior* to first-stage intensification. Second, the study requires data on the dates of prescription of second-line treatment, and those of lipid-lowering and antihypertensive medications *during* the period of second-line treatment. Third, for the period *after* clinicians have stopped prescribing second-line treatment, we require information on the prescription of subsequent anti-diabetic drugs and insulin, including newer alternatives such as Glucagon-like peptide-1s (GLP1s)

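### One one-year look-back covers chronic diagnoses as well as biomarkers, so, read as written, CVD or CHF coded earlier would count as absent

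*Protocol*

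**What the plan says.** Section 4 of the protocol, under Patient-level covariates, sets the window: "For the one-year period *prior* to second-line treatment, we will extract information on patient characteristics". The list in that sentence starts with demographic items ("age, gender, ethnicity, index of multiple deprivation, marital status, approximate duration of diabetes") and continues with "comorbidities (e.g. established CVD, CHF, CKD), and biomarker levels". One window therefore governs demographics, diagnoses and laboratory or clinical measurements alike. The section adds that each measure "will be considered as variables for the subgroup analysis and in reporting results according to baseline risk profiles", and that the covariate list "includes all those that will be required by the RAPIDS-UK model for predicting long-term effectiveness".

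Other sections rely on the same conditions:

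- The Brief literature review (section 2) makes pre-existing CVD the first hypothesised effect modifier.
- The sample size text of Objective 2 names the presence or absence of established CVD as a subgroup of prime interest.
- Objective 1 adjusts for histories of proteinuria and hypoglycaemia, and for comorbidities as they stand when second-line treatment starts. It gives no one-year limit.
- Objective 4 examines whether effects differ "according to age, baseline HbA1c, and the presence of different MLTC".
- Objective 5 lists "histories of CVD and hypoglycaemia" among the RAPIDS inputs and will report long-term results "both overall and stratified by baseline CVD status".

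**The concern.** A one-year window suits HbA1c, blood pressure, eGFR or BMI, which change and are measured again. It does not suit a diagnosis that may be entered once and not again. A patient with an infarction, a stroke or heart failure recorded three years before baseline, and nothing since, has no qualifying record in the window and is coded as not having the condition.

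The multiple imputation described under Missing data would not repair this. An absent code reads as no disease, not as a missing value.

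The variables affected are the ones that define the personalised results: the CVD subgroup, any MLTC profile built from the same extraction, and the CVD strata and starting histories in RAPIDS-UK. They also enter the covariate adjustment.

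**Working it through.** **Setting the sections side by side.** The protocol gives no figure to reproduce, so the first check is textual.

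| Place in protocol | How the condition is described | Look-back stated |
|---|---|---|
| Section 4, Patient-level covariates | established CVD, CHF, CKD, as examples | one year |
| Section 2, Brief literature review | pre-existing CVD | none |
| Objective 1 | histories; comorbidities at initiation | none |
| Objective 2, Sample size calculation | established CVD or not | none |
| Objective 5 | histories of CVD; baseline CVD status | none |

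The only stated window for diagnoses is one year, and every other use describes a condition that can have arisen at any earlier time. Nothing in the design forces the limit. Under Overall population, twelve months of prior registration is a minimum, not a cap. Under Treatment use, the protocol asks for full longitudinal drug histories, so it specifies longer histories where it wants them.

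**Illustration of size.** Let p be the true prevalence of a condition and s the share of those patients with a qualifying code in the one-year window. Neither is in the documents. I assume p = 10-30%, s = 50-90%, and no false positives.

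- Labelled without the condition: (1 - p) + p(1 - s) = 1 - ps.
- Of these, truly with the condition: c = p(1 - s) / (1 - ps).

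| c | s = 50% | s = 70% | s = 90% |
|---|---|---|---|
| p = 10% | 5.3% | 3.2% | 1.1% |
| p = 20% | 11.1% | 7.0% | 2.4% |
| p = 30% | 17.6% | 11.4% | 4.1% |

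For example, p = 30% and s = 50% gives 0.15 / 0.85 = 17.6%; p = 10% and s = 90% gives 0.01 / 0.91 = 1.1%. With s = 100%, c = 0.

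The labelled condition subgroup keeps a fraction s of its patients. If standard errors scale with the root of the sample size, the subgroup's standard error rises by 1/√s, which is 1.41 at s = 50% and 1.05 at s = 90%.

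**Effect on a subgroup contrast.** Let D1 be the treatment effect in captured patients with the condition, D0 the effect in those without it, and Dm the effect in missed patients. Treat each subgroup estimate as a patient-weighted average.

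- Labelled contrast: D1 - [(1 - c)D0 + cDm].
- True contrast: sD1 + (1 - s)Dm - D0.

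If Dm = D1, the labelled contrast is (1 - c)(D1 - D0), a loss of exactly c, or 1.1% to 17.6% over the table. If instead Dm = D0, the labelled contrast is D1 - D0 while the true one is s(D1 - D0), so the labelled contrast is too large by a factor 1/s. The direction therefore depends on who is missed.

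**The case against.** The strongest reply is that the sentence is loose drafting. It does not say that only codes dated within the year count. It also lists ethnicity and duration of diabetes, which cannot be confined to one year of records, and the Missing data section fills ethnicity from linked HES admissions without a time limit. Because the list is said to supply everything RAPIDS-UK needs, and RAPIDS needs histories, one can argue that histories are intended. A reader might infer from the window that established disease certainly will be missed; the documents do not support that. They support the conditional statement: it would be missed if the text is followed literally. This part of the reply stands, but it does not remove the point, because an analyst following the one stated rule would build the wrong variable.

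Other limits also stand:

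- CKD can partly be recovered from eGFR in the same window. CVD and CHF have no such substitute in the list.
- MLTC is not named in the covariate section. Applying the window to Objective 4 profiles is an inference, and the age and baseline HbA1c subgroups are untouched.
- The overall comparison in Objective 2 uses an instrument meant to handle unmeasured confounding, so the reach there is smaller.
- RAPIDS-UK will be calibrated to CPRD, which could absorb some error in level, though not patients placed in the wrong CVD stratum.
- A fixed year gives every patient the same ascertainment time, which is a real advantage.

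Finally, condition-level look-backs are often left to an analysis plan or code list, and only the protocol is at hand. That would answer a complaint about silence. Here the protocol is not silent: it states a window, and any later document would have to depart from it.

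**Conclusion.** The point holds as an internal inconsistency with a clear correction. The protocol states one one-year window for biomarkers and chronic diagnoses, nowhere widens it for diagnoses, and elsewhere depends on established or historical disease. The sections must be reconciled.

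The size cannot be fixed from the documents. Under the assumed 10-30% prevalence and 50-90% capture, about 1-18% of the group labelled as without a condition would truly have it, with no loss if capture is complete. A reader might go further and infer that CVD contrasts will be diluted by a known amount. That needs missed and captured patients to share the same treatment effect; if those missed respond more like patients without the condition, the contrast is exaggerated instead.

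**What to change.** Amend the Patient-level covariates text to say that comorbidities and event histories, including any diagnoses used for MLTC profiles, are ascertained from all available CPRD and linked HES records on or before the second-line start date, and that the one-year window applies to biomarkers. Keep the one-year comorbidity definition as a sensitivity analysis, which preserves a version with equal ascertainment time.

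The cost is small but not nil. Look-back length will vary with registration, with a twelve-month minimum. The data extract must also reach back to the earlier diagnosis records; the protocol does not state that it does, so this needs checking.
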